6.4.1.9. EudraCT Adverse Events Reporting

For the purpose of EudraCT reporting, the following tabulations will be created:

Frequency tabulations, by system organ class and preferred term, of the number (percent) of subjects with non-serious TEAE will be presented.

6.4.2. Laboratory Safety

6.4.2.1. Available Data

Laboratory tests scheduled are described in the protocol.

The statistical analyses will only present results in Standard International (SI) units. Other units will not be presented.

Only data provided by the central laboratory will be used in tables. Results from local labs will be listed only.

6.4.2.2. Derivation Rules

Fasted and Non-Fasted Results

Laboratory tests that are sensitive to the fasting status: glucose, triglycerides.

For these laboratory tests, only results from blood samples drawn in a fasted state will be included in the analysis. Results from blood samples taken in a non-fasted state will be listed only, no toxicities or abnormalities will be calculated. Laboratory results for which the fasting status is missing will be considered as taken non-fasted.

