EVENT	SCREENING PERIOD		TREATMENT PERIOD						FOLLOW-UP PERIOD	
	S1 ^a	S2	Day 1 ^b	W4	W12 and then every 12 weeks	W24 and then every 24 weeks	W48 ^c and then every 48 weeks	ED	EoT ^d	4 weeks after last IP dose (EoS)
	D-28 to D-1			± 3 days	± 7 days	± 7 days	± 7 days			± 3 days
Hematology		✓ ^{l, m}		✓	✓			✓	✓	✓
Chemistry		✓ ^{l, m}		✓	✓			✓	✓	✓
Lipid profile (fasted ⁿ)		✓ ^{l, m}				✓			✓	
Urine analysis		✓ ^{l, m}				✓			✓	
HBV DNA monitoring ^o		✓ ^l			✓				✓	
12-lead ECG		✓ ^l					✓		✓	
Serum immunoglobulin		✓ ^l				✓			✓	
CRP		✓ ^l		✓	✓			✓	✓	
Fecal calprotectin ^p	✓ ^q	✓ ^{l,r}		✓	✓			✓	✓	

^m Screening clinical laboratory results may only be available after randomization. In that case, these results will be reviewed after randomization and subjects with laboratory results meeting discontinuation criteria, will be discontinued from the study.

ⁿ Subjects should remain fasted for at least 8 hours, excluding water.

^o Only subjects with positive HBcAb and HBV DNA <LLOQ in a parent UC study will require ongoing HBV DNA monitoring every 12 weeks during the present study, and after study primary endpoint unblinding every 24 weeks.

^p Stool samples need to be taken prior to bowel preparation for endoscopy. Stool samples can be collected within 24 hours prior to the visit or during the visit.

^q FCP should be assessed during screening if the last assessment during SELECTION-LTE was >6 months prior to screening or the most recent value was >250 µg/g.

^r This FCP assessment should be obtained at the EoT visit in SELECTION-LTE (i.e. performed after the subject is fully eligible to roll over to the present study) and will be the baseline of the present study. In case FCP was not obtained at the EoT visit of SELECTION-LTE, an unscheduled stool sample should be collected within 24 hours prior to or during Day 1 (i.e. predose).

EVENT	SCREENING PERIOD		TREATMENT PERIOD						FOLLOW-UP PERIOD	
	S1 ^a	S2	Day 1 ^b	W4	W12 and then every 12 weeks	W24 and then every 24 weeks	W48 ^c and then every 48 weeks	ED	EoT ^d	4 weeks after last IP dose (EoS)
Study Day (D)/ Week (W)	D-28 to D-1			± 3 days	± 7 days	± 7 days	± 7 days			± 3 days
e-Diary instruction & review ^u			✓	✓	✓			✓	✓	✓
modified Mayo Clinical Score ^w	✓						✓	✓		

^a For subjects who consent to participate in the optional PK substudy, PK blood samples will be collected either at the Week 4 or Week 12 visit, or if more convenient, at any

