9.3.5.3. Clinical Laboratory Evaluations

Laboratory assessments will be analyzed descriptively. Changes from baseline and shifts according to normal ranges and/or a laboratory abnormality grading scale will be presented as well. Analyses will be done per treatment group.

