Appendix 3: Clinical Laboratory Assessments

Hematology	Chemistry	Urinalysis	Other
Hematocrit	Alkaline phosphatase	Appearance:	C-reactive protein (CRP)
Hemoglobin	Aspartate aminotransferase (AST)	Blood	Fecal (stool)
Platelet count	Alanine aminotransferase (ALT)	Color	Calprotectin
Red blood cell (RBC) count	Total bilirubin	Glucose	Bacterial stool culture
White blood cell (WBC) count	Direct and indirect bilirubin	Leukocyte esterase	Clostridium difficile toxin
Differentials (absolute and percentage), including:	Total protein	pH	Ova and parasites
Lymphocytes	Albumin	Protein	Serum biomarkers
Monocytes	Bicarbonate	Urobilinogen	Serum immunoglobulins
Neutrophils	Blood urea nitrogen		QuantiFERON® (or centrally reported equivalent assay)
Eosinophils	Calcium		Prothrombin time (PT)
Basophils	Chloride		Partial Thromboplastin time (PTT)
Reticulocyte count	Serum creatinine		International Normalized Ratio (INR)
Mean corpuscular volume (MCV)	Creatinine clearance (CrCl)		HBV DNA
	Cockcroft-Gault formula		
	Glucose		
	Phosphorus		
	Magnesium		
	Potassium		
	Sodium		
	Creatine phosphokinase (CPK)		
	Lipids (fasted)		
	Triglycerides		
	Cholesterol and its subfractions (high-density lipoprotein [HDL] and low-density lipoprotein [LDL])		

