^l Could be taken from SELECTION-LTE. In case assessments listed at S2 are conducted as part of the EoT visit in SELECTION-LTE, the assessments do not need to be repeated and assessment results may be used.

^m Screening clinical laboratory results may only be available after randomization. In that case, these results will be reviewed after randomization and subjects with laboratory results meeting discontinuation criteria, will be discontinued from the study.

EVENT	SCREENING PERIOD		TREATMENT PERIOD						FOLLOW-UP PERIOD	
	S1 ^a	S2	Day 1 ^b	W4	W12 and then every 12 weeks	W24 and then every 24 weeks	W48 ^c and then every 48 weeks	ED	EoT ^d	4 weeks after last IP dose (EoS)
	D-28 to D-1			± 3 days	± 7 days	± 7 days	± 7 days			± 3 days
Chemistry		✓ ^{l, m}		✓	✓			✓	✓	✓
Lipid profile (fasted ⁿ)		✓ ^{l, m}				✓			✓	
Urine analysis		✓ ^{l, m}				✓			✓	
HBV DNA monitoring ^o		✓ ^l			✓				✓	
12-lead ECG		✓ ^l					✓		✓	
Serum immunoglobulin		✓ ^l				✓			✓	
CRP		✓ ^l		✓	✓			✓	✓	
Fecal calprotectin ^p	✓ ^q	✓ ^{l, r}		✓	✓			✓	✓	

ⁿ Subjects should remain fasted for at least 8 hours, excluding water.

^o Only subjects with positive HBcAb and HBV DNA <LLOQ in a parent UC study will require ongoing HBV DNA monitoring every 12 weeks during the present study, and after study primary endpoint unblinding every 24 weeks.

^p Stool samples need to be taken prior to bowel preparation for endoscopy. Stool samples can be collected within 24 hours prior to the visit or during the visit.

^q FCP should be assessed during screening if the last assessment during SELECTION-LTE was >6 months prior to screening or the most recent value was >250 µg/g.

^r This FCP assessment should be obtained at the EoT visit in SELECTION-LTE (i.e. performed after the subject is fully eligible to roll over to the present study) and will be the baseline of the present study. In case FCP was not obtained at the EoT visit of SELECTION-LTE, an unscheduled stool sample should be collected within 24 hours prior to or during Day 1 (i.e. predose).

EVENT	SCREENING PERIOD		TREATMENT PERIOD						FOLLOW-UP PERIOD	
	S1 ^a	S2	Day 1 ^b	W4	W12 and then every 12 weeks	W24 and then every 24 weeks	W48 ^c and then every 48 weeks	ED	EoT ^d	4 weeks after last IP dose (EoS)
Study Day (D)/ Week (W)					± 3 days	± 7 days	± 7 days			± 3 days
	S1 ^a D-28 to D-1	S2	Day 1 ^b	W4	W12 and then every 12 weeks	W24 and then every 24 weeks	W48 ^c and then every 48 weeks	ED	EoT ^d	4 weeks after last IP dose (EoS)

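### SAP 6.4.2.2 tabulates and grades glucose only from samples recorded as fasted, but chemistry at Weeks 4, 12, 36 and EoS carries no fasting instruction, so many or most on-treatment glucose results are likely to be listed only

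*SAP*

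**What the plan says.** The rule is in SAP 6.4.2.2. It names the tests concerned: "Laboratory tests that are sensitive to the fasting status: glucose, triglycerides". It then restricts them: "For these laboratory tests, only results from blood samples drawn in a fasted state will be included in the analysis". The remaining results are set aside: "Results from blood samples taken in a non-fasted state will be listed only, no toxicities or abnormalities will be calculated". Unknown status falls on the same side: "Laboratory results for which the fasting status is missing will be considered as taken non-fasted".

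The sampling plan is in Protocol 8.9.1 and is repeated in SAP 2.4.1. Glucose is listed under chemistry in Protocol Appendix 3, where only the lipids carry a fasting label. The chemistry row has no fasting footnote. The lipid row does: "Subjects should remain fasted for at least 8 hours, excluding water". A separate footnote asks for sigmoidoscopy to be done fasting, following local guidance.

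Protocol 9.3.5.3 describes the laboratory analysis without any fasting condition: "Changes from baseline and shifts according to normal ranges and/or a laboratory abnormality grading scale will be presented as well". SAP 6.4.2.7 builds the worst-case tables from all non-missing post-baseline records and leaves out only local laboratory results.

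**The concern.** The analysis rule and the sampling schedule fit each other for triglycerides but not for glucose. Triglycerides are drawn with the fasted lipid profile, and their windows in SAP Table 4 are Weeks 24 and 48 only. Glucose is drawn at every chemistry visit, and SAP Table 2 sets chemistry windows at Weeks 4, 12, 24, 36 and 48. At three of those five visits nobody is asked to fast.

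Two things are at stake. First, the glucose summaries and abnormality counts may rest on a small part of the data collected, chosen by which visits happened to involve a fast. With 22 randomized subjects and an abbreviated report in which safety is a main remaining output, there is little to spare. Second, the rule works in both directions. A fasting restriction guards against meals raising glucose. It gives no reason to ignore a low value in a fed sample, yet such a value is also never classed as abnormal.

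**Working it through.** The documents give no figure on this point, so the check is a count of scheduled draws.

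**Inputs**
- Chemistry, including glucose: S2, Week 4, Week 12 and every 12 weeks, ED, EoT, EoS (Protocol 8.9.1; Appendix 3).
- Lipid profile with the 8-hour fast: S2, Week 24 and every 24 weeks, EoT (Protocol 8.9.1).
- Sigmoidoscopy done fasting: screening, Week 48 and every 48 weeks, and ED for anyone leaving the study before Week 48 (Protocol 8.9.1 footnotes).
- No general food restriction (Protocol 6.3.3).
- No subject reached Week 48 (SAP 6.1).

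**Formula.** Share without a fasting instruction = chemistry draws at visits with neither the lipid fast nor the sigmoidoscopy fast, divided by all scheduled post-baseline chemistry draws in the set.

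| Scheduled post-baseline chemistry draws | Draws | At a visit with a fasting instruction | Without |
|---|---|---|---|
| Before Week 48: W4, W12, W24, W36 | 4 | 1 (W24) | 3/4 = 75% |
| SAP Table 2 windows: the same plus W48 | 5 | 2 (W24, W48) | 3/5 = 60% |
| The same plus EoS | 6 | 2 (W24, W48) | 4/6 = 67% |
| Leaves before W12: W4, ED, EoS | 3 | 1 (ED) | 2/3 = 67% |
| Leaves between W12 and W24: W4, W12, ED, EoS | 4 | 1 (ED) | 3/4 = 75% |
| Leaves between W24 and W36: W4, W12, W24, ED, EoS | 5 | 2 (W24, ED) | 3/5 = 60% |
| Leaves between W36 and W48: W4, W12, W24, W36, ED, EoS | 6 | 2 (W24, ED) | 4/6 = 67% |

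Over the period actually observed, 60% to 75% of scheduled post-baseline draws have no fasting instruction, depending on when the subject leaves.

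**The ED sample.** For a subject leaving before Week 24, ED is the only post-baseline visit with any fasting instruction. It comes from the sigmoidoscopy, which states no number of hours and does not tie the blood draw to that fast. The ED sample may qualify but is not assured to. On the lipid fast alone, both early-leaver rows would have no qualifying draw. If a subject's last treatment visit were run as EoT instead of ED, the lipid fast would apply there and the count would be the same.

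**Baseline.** S2 carries the lipid fast, so baseline glucose should usually meet the rule. The loss is mainly after baseline.

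**Longer follow-up.** Over 216 weeks the share would be 10/19 = 53% with 12-weekly visits throughout, or 3/12 = 25% if visits became 24-weekly after Week 48. Neither applies to a study that stopped before Week 48.

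**The case against.** The case for leaving the rule alone is reasonable. Limiting a meal-sensitive test to fasted samples is a coherent choice. The laboratory analysis is descriptive, and glucose is neither an adverse event of interest (SAP Table 6) nor a listed risk (Protocol 5.5). Excluded values remain in the listings, which can be read in full for 22 subjects. Out-of-range results are also reviewed by the investigator, and clinically significant ones become adverse events whatever the fasting state (Protocol 8.4.2 and 11.1.5). All of this stands and keeps the point minor.

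A reader might also infer stronger versions, which the documents do not support:

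- *That fasting is required only at lipid visits, so no post-baseline glucose from an early leaver could ever be graded.* Sigmoidoscopy at ED is also done fasting. In addition, the SAP rule follows the recorded state of each sample, not the visit. A Week 4 or Week 12 sample drawn and recorded as fasted is analysed.
- *That only the Week 24 and Week 48 windows can be filled.* SAP 4.3.3 allocates samples by relative day to contiguous windows, so a qualifying ED sample fills whichever window it falls in.
- *That an empty glucose row would read as no abnormality.* Percentages use subjects with non-missing data (SAP 4.5.3), and continuous summaries show N (SAP 4.5.2). The gap appears as a reduced N.
- *That this is an undeclared change to the protocol.* Protocol 9.3.5.3 is silent on fasting, and Protocol 9 leaves methods to be detailed in the SAP. The rule adds detail and contradicts no protocol text, although no reason for it is given.

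**Conclusion.** The mismatch between SAP 6.4.2.2 and the sampling schedule is real, and its consequence is limited. Chemistry at Weeks 4, 12, 36 and EoS has no fasting instruction. Before Week 48 that covers 3 of the 4 scheduled on-treatment visits, and for a subject leaving before Week 24 it covers every post-baseline draw except ED. Many or most on-treatment glucose results are therefore likely to be listed only, and low values in non-fasted samples would be left unclassified.

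The shares describe scheduled visits, not results. How many results drop out depends on the fasting status recorded for each sample, which the documents do not show, and on any instruction in the separate laboratory manual, which was not available. The leaver counts assume that the subject attends both ED and EoS; without EoS, a subject leaving between Weeks 12 and 24 has 1 of 3 draws at a visit with a fasting instruction. This is a cheap improvement to the safety tables, and no conclusion of the study turns on it.

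**What to change.** Amend SAP 6.4.2.2 as follows.

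- Keep the fasted-only rule for triglycerides.
- Keep it for the by-visit glucose means, with a footnote naming the visits that carry a fasting instruction.
- In the worst-case and treatment-emergent abnormality tables, include all central-laboratory glucose results. Count low values regardless of fasting status. Show high values in two rows: fasted, and non-fasted or unknown.

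This brings glucose back into line with the input that SAP 6.4.2.7 already sets for the worst-case tables. The cost is SAP wording and one extra table row, with no new samples. The downside is that some non-fasted highs will reflect meals, which is why they have their own row.

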6.4.2.3. Definition of Toxicity Grades

Toxicity grades will only be derived for laboratory tests for which toxicity grades are available.

The CTCAE Version 5 will be used to assign toxicity grades (0 to 4) to laboratory results for analysis.

6.4.2.4. Definition of Non-Graded Abnormalities

For laboratory tests provided by the laboratory, the position of the actual analysis values versus their normal ranges will be determined directly by using the position indicator provided in the database as reported by the lab, expressing the classes for these analysis values as low (L), normal (N) or high (H). L, N and H are further referred to as non-graded abnormalities.

6.4.2.5. Urinalysis Tests with Categorical Results

Results of urinalysis with qualitative results will be tabulated by time point. No toxicity grading or non-graded abnormalities will be derived.

6.4.2.6. Treatment-Emergent Principle

Toxicity Grades

A post-baseline toxicity grade 1, 2, 3 or 4 is defined as treatment-emergent when higher than the toxicity grade of the baseline result. If the baseline result is missing, a post-baseline toxicity grade 1, 2, 3 or 4 will be considered as treatment-emergent.

Non-graded Abnormalities

A post-baseline non-graded abnormality class L or H is defined as treatment-emergent when it differs from the abnormality class of the baseline result. If the baseline result is missing, a post-baseline abnormality L or H will be considered as treatment-emergent.

6.4.2.7. Worst-Case Principle

Toxicity Grades

The worst-case post-baseline toxicity grade 0, 1, 2, 3 or 4 will be determined per subject, per laboratory test (and sense, if below and above), using all non-missing post-baseline records (including unscheduled and follow-up visits, but excluding local lab results).

The worst-case toxicity grade is the highest toxicity grade scored for the laboratory test (in each sense, if below and above).

Non-graded Abnormalities

The following worst-case post-baseline abnormalities L, N or H will be determined per subject, per laboratory test , using all non-missing post-baseline records (including unscheduled and follow-up visits, but excluding local lab results):

- L = low: at least one post-baseline result is classified as L.
- N = normal: all post-baseline results are classified as N.
- H = high: at least one post-baseline result is classified as H.

If, for a subject, both L and H are reported, the subject will be counted twice in the table: once with a worst-case L and once with a worst-case H.

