4.3.2. Analysis Phases

General Information

For each treated subject, analysis phases will be defined in order to embed the subject's event-type data and assessments (and other assessments as needed per analysis requirements).

Analysis phases describe patient-level segments (phases) of time throughout the conduct of a trial where the boundaries marking the end of one phase also denote the beginning of the next (seamless boundaries).

The last analysis phase will always end on the date of last contact in the study.

Applicable Analysis Phases

All event-type data (e.g., adverse events) and assessments will be allocated to analysis phases according to [Table 1](#).

Table 1 Analysis Phases

Analysis Phase	Start Analysis Phase	End Analysis Phase
Screening	Date of signing the ICF	Date of first study drug administration
Treatment	Date of first study drug administration	Date of last study drug administration + 30 days
Post-Treatment [#]	Date of last study drug administration plus 30 days	Date of last contact in the study

ICF: informed consent form

If the date of last study drug administration plus 30 days is after the date of last contact in the study, the study will not include a post-treatment phase. The last analysis phase will end on the date of last contact in the study.

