4.3.3. Analysis Windows

All assessments, including data collected on unscheduled visits, will be allocated to analysis windows based on the relative day of the assessment (see Section [4.3.1](#)).

If applicable, study assessments will be allocated according to one of the algorithms in the tables below.

Table 2 Analysis Windows for Laboratory Assessments (Hematology, Chemistry)

Analysis Window Label	Target Day	Interval Lower Bound	Interval Upper Bound
Baseline	1	-INF	1
Week 4	29	2	57
Week 12	85	58	127
Week 24	169	128	211
Week 36	253	212	295
Week 48	337	296	379

Table 3 Analysis Windows for FCP & CRP

Analysis Window Label	Target Day	Interval Lower Bound	Interval Upper Bound
Baseline	1	-INF	1
Week 4	29	15	43
Week 12	85	71	99
Week 24	169	155	183
Week 36	253	239	267
Week 48	337	323	351

Table 4 Analysis Windows for Lipid Profile, Urine Analysis, Serum Immunoglobin

Analysis Window Label	Target Day	Interval Lower Bound	Interval Upper Bound
Baseline	1	-INF	1
Week 24	169	2	253
Week 48	337	254	421

Definition of Baseline

Baseline is defined as the last non-missing value before the first study drug administration. Unless specified otherwise, if multiple values qualify as last value, the mean of these values will be used in the analysis for continuous values. For categorical values the best-case selection (e.g. normal instead of abnormal) will be used.

In case of re-escalation, a re-escalation baseline is defined as the last non-missing value before the first open-label study drug administration.

For electrocardiogram (ECG), where triplicate results are measured, the baseline is defined as the mean of the last recorded triplicate before the first study drug administration. If no triplicate is available before the first dose of study medication intake, the last ECG value will be considered as baseline.

Selection of Visits

Per parameter and analysis window, the value closest to the target date will be used in analysis tables and figures. Other values will be listed only. If more than one value is located at the same distance from the target day, then the latest in time will be selected. If - after the previous selection - still multiple values qualify, the mean of continuous values will be used in the analysis. For categorical values the worst-case selection will be used post-baseline.

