6.4	Frequency and severity of treatment-emergent adverse events (TEAEs), treatment-emergent SAEs, and TEAEs leading to treatment discontinuation.	Safety data will be summarized descriptively by treatment group according to the filgotinib dosing regimen actually received at randomization. For the primary safety analysis, any data collected after ES-confirmed UC flare will not be included in the analyses. For the secondary safety analysis, data will be included regardless of flare.	Only the primary safety analysis will be conducted. Vital signs and ECG data will be listed

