6.4.2.9. Presentation of Results

No formal inferential statistics (p-values) will be derived.

Continuous laboratory tests will be summarized by means of descriptive statistics (including 95% CI of the mean change) by laboratory test, treatment group and analysis window.

The analysis of abnormalities will focus on assessments reported during the treatment phase, i.e. the period during which events can be considered as treatment-emergent. Results reported outside of that period will only be listed.

A frequency table of the number (percent) of subjects with treatment-emergent worst-case abnormalities/toxicity grades per laboratory test, treatment group and analysis phase will be presented.

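### The SAP keeps only the safety analysis that stops at ES-confirmed flare, but its laboratory rules omit that cut, so open-label 200 mg values can be tabulated under 100 mg

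*SAP*

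**What the plan says.** **The general rule.** The safety row of SAP Table 5 (Section 6.1) describes the planned primary safety analysis as one where "any data collected after ES-confirmed UC flare will not be included in the analyses". Its revised-analysis column states "Only the primary safety analysis will be conducted", followed by "Vital signs and ECG data will be listed". The row is keyed to SAP 6.4 as a whole. Protocol 9.3.5 gives the same definition for safety data and names laboratory assessments among them.

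**The laboratory rules.**
- SAP 6.4.2.7 derives worst-case toxicity grades and low/normal/high classes "using all non-missing post-baseline records (including unscheduled and follow-up visits, but excluding local lab results").
- SAP 6.4.2.9 says "The analysis of abnormalities will focus on assessments reported during the treatment phase". In SAP Table 1 that phase ends at "Date of last study drug administration + 30 days", with no break at re-escalation.
- SAP 6.4.2.9 summarizes continuous tests by analysis window, and under SAP 4.3.3 "All assessments, including data collected on unscheduled visits, will be allocated to analysis windows based on the relative day of the assessment".
- SAP 6.4.2.8 tabulates AST, ALT and bilirubin without a flare limit.

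**Supporting rules.** SAP 4.3.3 treats the re-escalation product as study drug: "a re-escalation baseline is defined as the last non-missing value before the first open-label study drug administration". SAP 4.5.1 presents groups as randomized whatever the later switch to open-label 200 mg. The adverse event section (SAP 6.4.1.8) and the CRP/FCP section (SAP 6.3.2) both state a cut at ES-confirmed flare.

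**The concern.** The retained safety analysis is defined by the flare cut, yet the laboratory sections select records by a different rule. If a 100 mg subject flares and is re-escalated, later laboratory values reflect open-label 200 mg but would enter the 100 mg means, worst-case grades and liver counts. The same subject's adverse events would stop at the flare in the tables. In a study that compares two doses, the two main safety displays would then cover different periods, and one would assign 200 mg exposure to the 100 mg column.

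The re-escalation schedule also adds blood draws, so a flaring subject has more chances to reach a worst-case grade than one who stays in remission.

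Flares in the 200 mg arm do not change the dose, but their later laboratory values would still be tabulated, contrary to the retained analysis.

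**Working it through.** The plan states no figure on this point, so the check is to run a subject through the SAP rules.

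**Do the limits in the text remove post-flare records?**

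| Display | Limit stated | Stops at flare? |
|---|---|---|
| Adverse events (SAP 6.4.1.8) | Treatment phase, up to ES-confirmed flare | Yes |
| CRP and FCP (SAP 6.3.2) | Post-flare data listed only | Yes |
| Worst-case laboratory results (6.4.2.7) | Post-baseline, non-missing, central laboratory | No |
| Laboratory abnormality tables (6.4.2.9) | Treatment phase | No |
| Laboratory means (6.4.2.9, 4.3.3) | Analysis window | No |
| AST, ALT, bilirubin (6.4.2.8) | Post-baseline visit and same treatment, for the Hy's Law definition only | No |

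To test the treatment-phase limit, assume a 100 mg subject with flare on Day 100, open-label 200 mg from Day 101 and last dose on Day 200. The phase ends at Day 200 + 30 = Day 230. Draws on Days 129, 157 and 185 (re-escalation Weeks 4, 8 and 12) and Day 228 (follow-up, 4 weeks after last dose) all fall inside it. Days 129, 157 and 185 lie in the Week 24 window (128 to 211) and Day 228 in the Week 36 window (212 to 295). All four are eligible for the 100 mg tables. With the adverse event cut, only Days 29 and 85 would be.

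**How many draws are affected?** Inputs: hematology and chemistry at Weeks 4, 12, 24 and 36 (SAP 2.4.1), and at re-escalation baseline and re-escalation Weeks 4, 8 and 12, then the next 12-weekly visit (SAP 2.4.2). Assumptions: re-escalation starts in the flare week, visits fall on target, and there are no unscheduled or follow-up draws. Follow-up to Week 36 is assumed because SAP 6.1 says no subject reached the Week 48 time point. Day = 7 × week + 1.

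For a flare at Week 12:
- Blinded draws: Day 29 and Day 85, the latter also being the re-escalation baseline.
- Open-label draws: Days 113, 141, 169 and 253.
- Open-label share: 4/6 = 67%.

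Under SAP Table 2, Day 85 is kept for Week 12 (target 85), Day 169 is selected for Week 24 (target 169) and Day 253 for Week 36 (target 253). Both later window means therefore use open-label values. Day 113 falls in the Week 12 window and is not selected for the mean, but it still counts toward the worst case.

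| Flare week | Draws to Week 36 | On open-label 200 mg | Share |
|---|---|---|---|
| 8 | 7 | 5 | 71% |
| 12 | 6 | 4 | 67% |
| 16 | 7 | 4 | 57% |
| 20 | 7 | 4 | 57% |
| 24 | 6 | 3 | 50% |

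A subject without flare has 4 draws, so the Week 12 case has 6 − 4 = 2 extra chances for a worst-case grade.

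**What does one subject move?** SAP 2.4.3 gives 22 randomized; the split is not reported. With 11 per arm, 1/11 = 9.1 percentage points. With 12 or 10 in the arm it is 8.3 or 10.0.

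**The case against.** The strongest reply is that Table 5 and Protocol 9.3.5 already govern laboratory data. On that reading the exclusion is pre-specified, and a subsection that does not repeat it does not repeal it. SAP 6.4.2.7 could be read as saying only which kinds of record qualify. This does not remove the conflict: SAP 6.4.2.9 is not silent, but sets its own limit at the treatment phase, where the parallel adverse event sentence adds the flare. A programmer following the laboratory text as written would include post-flare records. If Table 5 prevails, the laboratory text contradicts it and still needs correcting.

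Two further replies carry some weight. The CRP/FCP section is an efficacy section under another row of Table 5, so the adverse event section is the only like-for-like comparator. SAP Section 1 also refers to a Programming Requirements Document that is not available here, and some lines just before the start of the safety section are unreadable in the public copy. A filter could be stated in either place, but it cannot be presumed.

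The objection on consequence stands in part. The trial stopped early, the report is abbreviated, no formal testing is done, and the safety endpoint is adverse events. The figures above describe a hypothetical subject, and one subject moves a percentage by 9 points only if an open-label value is worse than every blinded one. There is also a real trade-off: a strict cut could leave a liver abnormality that first appears on open-label 200 mg visible only in listings.

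**Conclusion.** The concern holds. As written, the laboratory rules produce tables that differ from the only safety analysis the SAP retains, and post-flare values on open-label 200 mg would be shown under 100 mg. It should be fixed, though the reach is limited to descriptive laboratory tables, since vital signs and ECG are only listed.

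The actual size is unknown because the documents do not report flares. If no 100 mg subject was re-escalated, no 200 mg value enters the 100 mg column. Where one was, half to about 70% of that subject's scheduled draws could be on open-label drug (flare at Weeks 8 to 24, follow-up to Week 36), and a changed worst-case category moves the arm percentage by about 9 points, assuming 11 per arm.

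A separate, minor mismatch remains. SAP 4.2 groups safety data as randomized, while Protocol 9.3.5 and the planned-analysis column of Table 5 use the regimen actually received at randomization, and Table 5 does not declare the change. It matters only for initial mis-dispensing, which SAP 4.2 already lists, and not for re-escalated subjects.

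**What to change.** In SAP 6.4.2.7 to 6.4.2.9, restrict laboratory means, worst-case grades and classes, and hepatotoxicity tables to central-laboratory records up to ES-confirmed flare, matching SAP 6.4.1.8. List later records, or tabulate them as a separate re-escalation phase against the re-escalation baseline that SAP 4.3.3 already defines but no laboratory rule uses. The separate tabulation is the better choice for liver tests, because it keeps abnormalities that first appear after re-escalation in view. Align SAP 4.2 with Protocol 9.3.5 on grouping, or declare the change in Table 5.

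The cost is a few lines of SAP text and one date filter, with no new data. Some values would move from tables to listings, and late windows may fall to a single subject, which SAP 4.5.2 does not tabulate.
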